Study Title: Does a Different Local Anesthetic Improve Pain After Carpal Tunnel Release?

NCT number: 04833777

Document date: November 27, 2023

Document: Study protocol, statistical plan, and summary of results

Does addition of longer-acting local anesthetic improve the post-operative pain after carpal tunnel release? A randomized controlled study

Principal investigator: [name]

Sub-investigators: [name] (resident), [name], [name], [name] (resident)

Background and rationale

Carpal tunnel syndrome, the most common compressive neuropathy of the upper extremity, has been shown to cause significant functional and occupational disability. This condition is caused by compression of the median nerve at the wrist, leading to pain, numbness, tingling, and finger weakness. While non-operative management can improve symptoms, definitive management of refractory cases involves carpal tunnel release (CTR)—the surgical division of the transverse carpal ligament overlying the median nerve. Historically, this procedure was performed in the operating room under general anesthetic or conscious sedation. However, in recent years many surgeons in Canada have transitioned to performing CTR in the clinic under wide-awake local anesthesia with no tourniquet (WALANT)(1). This technique has been shown to provide a near painless experience during CTR. Additionally multiple studies have demonstrated improved patient satisfaction and significant benefits in cost-savings compared to other methods (2-4).

In our clinic, CTR is performed under WALANT. This involves superficial infiltration of the incision site with 10mL of 1% lidocaine with 1:100,000 epinephrine and 1mL of 8.4% sodium bicarbonate. A previous study by the senior author ([name] et al., manuscript in preparation, REB Bio 1439), maximal pain was experienced 8 hours after CTR (Visual Analogue Scale (VAS) pain score 1.91 at 2 hours, 4.65 at 8 hours, 3.81 at 24 hours).

Lidocaine is the most common local anesthetic (LA) used for CTR due to its rapid onset of action (2-5 minutes) and efficacy in pain blockade. However, it has a relatively short half-life and duration of pain relief is only 50-120 minutes (60-180 minutes when combined with epinephrine)(5). Some surgeons (including the senior author) will add sodium bicarbonate to the anesthetic, as it has been shown to increase the duration of LA, as well as decrease pain during initial administration(6, 7).

Longer-acting agents alone (e.g. bupivacaine) are less often used in the outpatient setting for local anesthetic due to a slightly longer onset of action (5-10 minutes). However, duration of pain relief can last up to 8 hours(5). As such, a reasonable compromise might be to use a solution that combines a short- and longer-acting agent. A previous randomized controlled trial by Pressman et al. showed that subcutaneous infiltration of 2% lidocaine with epinephrine + 0.5% bupivacaine or 0.5% ropivacaine resulted in lower pain scores at 4 and 6 hours after CTR compared with lidocaine with epinephrine alone(8). No other RCTs have been performed studying the effects of different local anesthetics on post-op pain for CTR. Furthermore, no studies have compared the effects of these anesthetics with the addition of bicarbonate. Therefore, the aim of our study is to determine whether a combination of lidocaine + bupivacaine with epinephrine and bicarbonate provides increased pain relief compared with lidocaine with epinephrine and bicarbonate (current regimen) over the first 24 hours after CTR.

Research question: Does the addition of bupivacaine to the current LA regimen of lidocaine with epinephrine and bicarbonate provide increased pain relief compared for carpal tunnel release? Secondarily, does this new anesthetic regimen affect eventual outcome at 3 months?

Methods

Study design: Prospective randomized control trial

A research nurse will meet with each patient presenting for outpatient CTR surgery at the Saskatoon City Hospital procedure room. The following exclusion criteria will be applied: age <18 years, repeat CTR on the same side, simultaneous procedures for other hand/wrist pathology, and patients with rheumatoid arthritis or a history of trauma or surgery to the local area.

The research nurse will obtain informed consent for interested participants. The patient will be assigned a subject number and be randomized to standard vs. bupivacaine treatment based on a computer algorithm. Participants will complete the Boston Carpal Tunnel Questionnaire as a baseline for comparison as well as a brief questionnaire on demographics. For those patients that are having both sides released during the study period, the first side will be randomized based on the study protocol and the second side will be anesthetized with the other treatment. They will be blinded to both procedures such that we can directly compare their operative experience.

The surgeon ([name] or [name]) will draw up and mix the pre-determined anesthetic for each patient based on the randomization protocol. The research nurse (who will be performing all assessments) and the patient will remain blinded to the type of anesthetic.

The two types of anesthetic will be:

- 1) 10mL 1% lidocaine with 1:100,000 epinephrine and 1mL 8.4% sodium bicarbonate (standard treatment)
- 2) 5mL 1% lidocaine with 1:100,000 epinephrine + 5mL 0.5% bupivacaine with 1:100,000 epinephrine and 1mL 8.4% sodium bicarbonate (bupivacaine treatment)

The participants will be anesthetized in the standard fashion, with all 11mL of LA infiltrated subcutaneously into the area of the incision. After a delay of 20-40 minutes, the CTR will be carried out using the standard mini-open approach. Patients will be provided with the standard post-operative instructions regarding activity and wound care.

After the procedure, participants will complete a short questionnaire (VAS) about any pain experienced during the administration of the local anesthetic and during the procedure. Patients will be sent home with instructions to complete a pain and numbness assessment at 2, 4, 6, 8, 10, 24, 48, and 72 hours after surgery. They will be provided with a form containing the VAS and numbness scale and the times at which they are to self-administer these questionnaires. Additionally, they will be provided with 20 Tylenol tablets (325mg each) and 20 ibuprofen tablets (200mg each), with instructions to take 1-2 tablets of one or both analgesics every 6 hours as needed during the first 72 hours. They will be asked to document the times at which they took the medications, as well as the dosages taken. They will be asked to refrain from using other types of pain medications, if possible. They will also be asked to document use of any other analgesics including Cannabis. Any questions will be answered by the research nurse before leaving clinic.

The day after surgery, at the 24 hour mark, the research nurse will call each patient and inquire about their pain scores and numbness at 2, 4, 6, 8, and 10 hours, as well as the present time (24 hours). He or she will also ask about the number of Tylenol and/or ibuprofen pills taken during the first 24 hours, as

well as the timing of consumption. The research nurse will call the patient again at the 72 hour mark to ask about pain and analgesic consumption between 24-72 hours post-surgery. This information recorded on a password-protected datasheet which contains only the subject number (no identifiers).

The patient will return for their standard follow-ups. At 3 months, the research nurse will repeat the Boston Carpal Tunnel Questionnaire to assess outcome. At this time, if the patient wishes, they may be unblinded.

For patients wishing for bilateral CTR, the first will be performed according to the randomization protocol as described above. The contralateral CTR will be performed 2-8 weeks later (as standard in our practice), with the alternate anesthetic (e.g. first CTR with standard treatment, second CTR with bupivacaine treatment). The same post-operative assessment will be performed for the second CTR. Patients will remain blinded to their type of anesthetic in each wrist until 3 months after the second surgery is performed. At that time, they will be asked by the research nurse whether the first or second surgery provided a better pain experience. Only after this will they be unblinded, if desired.

Statistical analyses:

Based on power analysis, the minimum number of participants needed is 128. Assuming a 10% attrition rate, we aim to recruit 140 participants (70 in each group).

Descriptive statistics will be used to show the patient characteristics of each treatment group. We will compare VAS scores at injection, and 2, 4, 6, 8, 10, 24, 48, and 72 hours after surgery. Additionally, we will compare the amount of post-op oral analgesia (number of Tylenol and/or ibuprofen tablets) required in each group, and the time to first consumption. Finally, we will compare the pre- and post-surgery Boston Carpal Tunnel scores between the two groups. Continuous variables will be analyzed with an independent samples t-test or ANOVA, and categorical variables with a chi-square test.

Results overview

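### Regular analgesic use before surgery is not a specified baseline item or covariate, so habitual doses add avoidable noise to tablet count and modestly attenuate time to first analgesic

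*Combined protocol and SAP*

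**What the plan says.** The Methods section (Study design) gives baseline data collection one sentence: "Participants will complete the Boston Carpal Tunnel Questionnaire as a baseline for comparison as well as a brief questionnaire on demographics". The items of the demographic form, described only as "a brief questionnaire on demographics", are not listed. The exclusions cover minors, repeat release on the same side, simultaneous hand or wrist procedures, and "patients with rheumatoid arthritis or a history of trauma or surgery to the local area". Regular users of pain medicine are therefore eligible.

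After surgery, patients go home with Tylenol and ibuprofen, "with instructions to take 1-2 tablets of one or both analgesics every 6 hours as needed during the first 72 hours". On recording, the protocol says: "They will be asked to document the times at which they took the medications, as well as the dosages taken". On other drugs it says: "They will be asked to refrain from using other types of pain medications, if possible", and "They will also be asked to document use of any other analgesics including Cannabis". No field is described for the reason for a dose, or for doses taken before surgery.

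The Statistical analyses section then compares "the amount of post-op oral analgesia (number of Tylenol and/or ibuprofen tablets) required in each group, and the time to first consumption". The tests named are the t-test, ANOVA and chi-square. No covariate or stratum is mentioned, and no rule says how habitual doses of the same two drugs are handled. The Results overview reports time to first analgesic use (5.2 h with bupivacaine, 3.7 h in controls, p=0.02) and gives no tablet-count result.

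**The concern.** Both analgesic outcomes are meant to show how much relief the block gives and when it wears off. For someone who already takes acetaminophen or ibuprofen regularly, some tablets, and possibly the first one, follow routine instead.

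Such patients are plausible in this trial. The Background describes carpal tunnel syndrome as a painful condition and release as treatment for refractory cases. Rheumatoid arthritis is the only systemic painful disease excluded. Patients having both sides done have the second wrist released 2-8 weeks after the first, so that wrist is still untreated during their first 72-hour record.

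At stake is precision in two planned comparisons, one of which is among the few results reported. If regular use is not recorded before surgery, its effect can be neither measured nor adjusted for afterwards.

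**Working it through.** **Inputs from the protocol.** Minimum sample 128 and target 140 (Statistical analyses). Analysed groups of 67 and 72, and times of 5.2 h and 3.7 h with p=0.02 (Results overview). The share of regular users, h, their habitual tablet number, m, and the tablet SD, s, are not given. All three are assumed below and shown over a range.

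**1. The plan's own figure.** The inputs to the power analysis are not stated, so 128 cannot be reproduced from the document alone. Assuming an effect of d = 0.5 SD, two-sided alpha 0.05 and 80% power, the normal approximation 2(1.960+0.842)²/0.5² gives 62.8, so 63 per arm or 126. The t-test calculation gives 63.8, so 64 per arm or 128. I use d = 0.5 and 64 per arm (power 80.1%) as the reference.

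**2. Tablet count, habitual doses added to need-based doses.** Habitual tablets have the same expectation in both arms, so the expected arm difference stays at 0.5s. The variance becomes s² + h(1-h)m². Example with s=6, m=12, h=20%: 36 + 0.2×0.8×144 = 59.04, SD 7.68, d = 3/7.68 = 0.39, power 59.2%.

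| s | m | h=10%: d, power | h=20%: d, power | h=30%: d, power |
|---|---|---|---|---|
| 6 | 6 | 0.479, 76.7% | 0.464, 74.1% | 0.455, 72.3% |
| 6 | 12 | 0.429, 67.3% | 0.390, 59.2% | 0.369, 54.4% |
| 4 | 6 | 0.456, 72.6% | 0.429, 67.3% | 0.412, 63.8% |
| 4 | 12 | 0.372, 55.0% | 0.320, 43.5% | 0.294, 37.9% |

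**3. Tablet count, habitual doses replace need-based doses entirely.** Regular users then show no arm difference and d becomes 0.5(1-h), with the SD held fixed. For h = 10, 20 and 30% this gives 0.45, 0.40 and 0.35, with power 71%, 61% and 50%. Of the models considered, only this one shrinks the tablet difference itself.

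**4. Time to first analgesic.** The recorded time is the smaller of the need-based time and the habitual time, so a habitual dose matters only if it comes first. For scale, take an undiluted difference of 1.5 h. The SD is back-calculated from the reported p-value: t on 137 df is 2.354, SE = 1.5/2.354 = 0.637 h, and SD = 0.637/√(1/67+1/72) = 3.75 h. This assumes that all 139 patients contributed a time, which the document does not say. With gamma-distributed need-based times, the simulated difference among regular users is 0.55 h if the habitual dose falls uniformly within 0-6 h, and 0.94 h if within 0-12 h. The overall difference is (1-h)×1.5 + h×(that value):

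- 0-6 h: 1.41, 1.31 and 1.22 h at h = 10, 20 and 30%.
- 0-12 h: 1.44, 1.39 and 1.33 h.

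Direct simulation of the whole sample agrees to within about 0.01 h.

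**5. What a baseline covariate recovers.** In step 2, if every regular user added the same m, a yes/no covariate would absorb h(1-h)m² and return d to 0.5 and power to about 80%. Habitual amounts that differ among regular users are not absorbed, so recovery is partial in practice. Simulation at 64 per arm with 10-20% regular users gave 59-76% power unadjusted and 68-80% adjusted for tablets. For time to first analgesic it gave about 74% and 77%. The starting level depends on the effect assumed, so only the small gain is informative.

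**The case against.** The strongest reply is that this asks for one more covariate, of unknown value, in outcomes that come after the pain scores. Randomisation balances habitual use in expectation. Patients are told to take the supplied tablets as needed and to avoid and record other analgesics, so habitual users of other drugs add nothing directly to the tablet count. All doses with recorded times make a legitimate and fairly objective outcome. Most of this stands. It limits the point to precision and modest attenuation, but does not remove it.

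A reader might infer more than the documents support:

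- **That regular use was not asked.** The demographic items are not listed. Only non-specification can be shown.
- **That both arm differences shrink in proportion to the share of regular users.** That is the full-replacement case in step 3. Additive doses leave the expected tablet difference unchanged, and time to first dose shrinks less.
- **That the reported 1.5 h result should be shrunk further, or that its significance is in doubt.** The result was observed in the patients enrolled, so it already contains whatever dilution they brought. Step 4 shows scale only.
- **That the pain-score comparison is affected.** How tablets are counted does not directly touch the VAS scores.
- **That only doses taken for the operated hand should count.** That attribution is subjective and made after randomisation. The Results overview reports more numbness with bupivacaine at nearly all time points, which could hint at allocation. A tablet taken for another reason also relieves the hand, and a patient's carpal tunnel pain may itself be in that hand.

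**Conclusion.** The point holds as a modest, inexpensive improvement. The protocol specifies no baseline record of regular analgesic use, and no adjustment for it, in two outcomes that depend on it. There is no systematic bias between arms, although chance imbalance could move a difference either way. The expected cost is extra variance in tablet count, a smaller tablet difference only to the extent that habitual doses replace need-based ones, and modest attenuation of time to first analgesic.

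The size cannot be established from the documents. The ranges above rest on assumed values of 10-30% regular users, 6-12 habitual tablets, a tablet SD of 4-6 and a 0.5 SD effect. If few patients are regular users, the loss is small and so is the gain from adjusting.

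**What to change.** Add one baseline item: regular analgesic or cannabis use in the past week, and the last dose before surgery. Prespecify regular use (yes/no) as a covariate in the tablet-count and time-to-first-analgesic comparisons, for example by linear regression in place of the unadjusted t-test. State that all recorded doses of the two supplied drugs form the main outcome. Add a sensitivity analysis excluding baseline regular users. Because that exclusion rests on a pre-treatment characteristic, it keeps the randomised comparison, but at 20% regular users it would leave about 64×0.8 = 51 per arm. A tick box for doses taken for the operated hand, if wanted, should be supportive only. None of this changes what patients may take.

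The cost is one question and one degree of freedom. Results are already reported, so the new item can help only a repeat or later use of the design. For this trial, the report should state how doses were counted, say whether regular use was in fact recorded, and name its absence as a limitation if it was not.

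### The 3-month Boston comparison has no baseline covariate although the baseline score is collected, so the secondary question is in general answered less precisely than the data allow

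*Combined protocol and SAP*

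**What the plan says.** The research question asks, secondarily, whether the new regimen changes outcome at 3 months. The Methods provide both measurements needed: "Participants will complete the Boston Carpal Tunnel Questionnaire as a baseline for comparison", and later "At 3 months, the research nurse will repeat the Boston Carpal Tunnel Questionnaire to assess outcome".

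The Statistical analyses section gives the comparison in one sentence: "Finally, we will compare the pre- and post-surgery Boston Carpal Tunnel scores between the two groups". The method follows: "Continuous variables will be analyzed with an independent samples t-test or ANOVA". No ANCOVA, regression model or covariate is named, and the section does not say whether the quantity compared is the 3-month score or the change from baseline.

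For patients having both hands released, "the first side will be randomized based on the study protocol and the second side will be anesthetized with the other treatment". On timing, "The contralateral CTR will be performed 2-8 weeks later", and "Patients will remain blinded to their type of anesthetic in each wrist until 3 months after the second surgery is performed".

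The Results overview gives 67 control and 72 intervention patients and reports no Boston result.

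**The concern.** The baseline score is collected, but the named methods either ignore it or use it with a fixed weight. A t-test on the 3-month score ignores it. A t-test on change subtracts it in full. A two-time-point ANOVA with a group-by-time term is the same test as the t-test on change. None is biased under randomisation if all patients are scored or missingness is ignorable, but each is in general less precise than estimating the weight from the data, as ANCOVA does.

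Precision matters here because a finding of no difference at 3 months is informative only through what its interval excludes. A wider interval excludes less.

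A smaller, separate point concerns bilateral patients. They receive the other regimen 2 to 8 weeks after the first surgery, and 3 months is about 13 weeks. By any 3-month score, timed from either surgery, they have had both regimens. The plan does not say which hand or which surgery that score refers to.

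**Working it through.** **The plan's own figure.** The minimum of 128 patients is stated without alpha, power, effect size or SD. It reproduces as 64 per group for a t-test if one assumes a standardised difference of 0.5, two-sided 5% and 80% power. Nothing ties it to the Boston score, so it is not used below.

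**Inputs.** Group sizes 67 and 72 (Results overview). Assumed, because the documents do not give them: r, the correlation between baseline and 3-month scores, at 0.3, 0.5 and 0.7; and k, the baseline SD divided by the 3-month SD, at 0.8, 1 and 1.25. All results are in units of the SD of the 3-month score.

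**Variance.** Subtracting b times the baseline from the 3-month score gives variance, relative to the 3-month score alone, of 1 + b²k² − 2brk.
- 3-month score only, b = 0: 1.
- Change, b = 1: 1 + k² − 2rk.
- ANCOVA, b = r/k, the minimising value: 1 − r².

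In large samples ANCOVA is therefore never less precise. It ties with the 3-month score alone only at r = 0, and with change only at k = r.

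**3-month score only.** SE = √(1/67 + 1/72) = 0.1697; t on 137 df = 1.977; half-width 0.1697 × 1.977 = 0.336.

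**Half-widths of the 95% interval**, each 0.336 times the square root of the relative variance (shown in brackets):

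| Analysis | r = 0.3 | r = 0.5 | r = 0.7 |
|---|---|---|---|
| 3-month score only | 0.336 (1) | 0.336 (1) | 0.336 (1) |
| Change, k = 0.8 | 0.362 (1.16) | 0.308 (0.84) | 0.242 (0.52) |
| Change, k = 1 | 0.397 (1.40) | 0.336 (1.00) | 0.260 (0.60) |
| Change, k = 1.25 | 0.452 (1.81) | 0.385 (1.31) | 0.303 (0.81) |
| ANCOVA | 0.320 (0.91) | 0.291 (0.75) | 0.240 (0.51) |

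**Cost of estimating the slope.** Multiplying the ANCOVA variance by 1 + 1/135 and using 136 df gives 0.321, 0.292 and 0.241, and 0.337 at r = 0. ANCOVA starts to gain on the 3-month score alone at about r = 0.09.

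**Simulation.** With 5,000 trials per r, 67 against 72 patients and equal SDs, mean half-widths were 0.335–0.336 (3-month score only), 0.396, 0.336 and 0.259 (change) and 0.321, 0.292 and 0.240 (ANCOVA). These agree with the formulas.

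**Difference detectable with 80% power** (noncentral t). 3-month score only: 0.479 SD. ANCOVA: 0.457, 0.415 and 0.342 SD. Change with k = 1 scales as the square root of the relative variance: 0.479 × √1.40 = 0.567, 0.479 × √1.00 = 0.479, 0.479 × √0.60 = 0.371 SD.

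**If 10% have no 3-month score**, the attrition the plan assumes: 0.9 × 67 ≈ 60 and 0.9 × 72 ≈ 65; SE 0.1790; t on 123 df = 1.979; half-width 0.354. ANCOVA gives 0.338, 0.307 and 0.253.

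**The case against.** The size of the gain is assumed throughout, since neither r nor k is in the documents. Change from baseline is at least as natural a reading of the plan as the 3-month score alone, and on that reading the gain can vanish: at r = 0.7 and k = 0.8 the half-widths are 0.242 for change and 0.241 for ANCOVA after counting the fitted slope. Against the 3-month score at r = 0.3 the gain is under 5%. The planned test is valid, the outcome is secondary, and an ANCOVA chosen now is post hoc. Randomisation also protects the comparison only if all patients are scored or missingness is ignorable, and the plan names no missing-data method. Finally, the bilateral question concerns which contrast is measured, arguably a weightier matter than precision.

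Much of this stands. The gain cannot be given as one number, the attrition caveat is right, and the bilateral point is distinct. One record per patient by first-side regimen is also an inference: the documents favour it but do not state it, and the post-operative assessment is repeated for the second side.

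It does not remove the concern. Whether the 3-month score or change is the better choice depends on the unknown r and k: at k = 1, change is the worse at r = 0.3 and the better at r = 0.7. ANCOVA avoids that choice and loses only a negligible amount when r is near zero. Being post hoc calls for a label; it is no reason to withhold the more precise estimate.

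**Conclusion.** The concern holds as a point of efficiency and clarity. Under equal SDs and r from 0.3 to 0.7, ANCOVA shortens the interval by 4.6% to 28.6% relative to the 3-month score alone, and by 19.4% down to 7.8% relative to change. At r = 0.5 the variance falls by a quarter, so 0.75 × 128 = 96 patients would give the precision of 128 analysed without adjustment.

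These figures rest on assumed correlations and, except where attrition is shown, on all 139 patients being scored. The pain comparisons are unaffected. With no Boston result reported, no wrong conclusion follows. The change should be made, but the trial's validity does not turn on it.

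**What to change.** - Name the 3-month Boston score as the outcome. Analyse it by ANCOVA with the baseline Boston score as covariate, by the regimen randomised for the first side, one record per patient. Report the adjusted difference with its 95% interval.
- Label the ANCOVA as added after results were reported, and show any t-test or ANOVA already run beside it.
- Report how many patients per group have both scores.
- For bilateral patients, state which hand and which surgery the 3-month score refers to, and give their number per group. If only a score timed from the second surgery, or a patient-level score, exists, say so and note that they had received both regimens by then.
- Label any sensitivity analysis excluding bilateral patients as post hoc. Note that it excludes on a decision made after randomisation unless bilateral surgery was planned at enrolment.

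The cost is one analysis sentence and a re-run on scores the protocol already collects, with no new visits. ANCOVA uses one degree of freedom, and patients without a baseline score drop out unless handled. The documents do not show whether a first-hand score timed from the first surgery exists for bilateral patients; if it does not, stating which score was used is the whole of that remedy.

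### Post-operative VAS is compared without adjustment although a baseline Boston score is already collected; adjusting for it could add precision at almost no cost, by an amount the documents do not let us fix

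*Combined protocol and SAP*

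**What the plan says.** The Statistical analyses section defines the pain comparison: "We will compare VAS scores at injection, and 2, 4, 6, 8, 10, 24, 48, and 72 hours after surgery". The method is one sentence covering all outcomes: "Continuous variables will be analyzed with an independent samples t-test or ANOVA", with a chi-square test for categorical ones. No covariate, regression or mixed model appears anywhere in the document, so the mention of ANOVA cannot be read as ANCOVA.

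Baseline information is collected. Under Methods, "Participants will complete the Boston Carpal Tunnel Questionnaire as a baseline for comparison as well as a brief questionnaire on demographics". The only stated analytic use of the Boston score is: "Finally, we will compare the pre- and post-surgery Boston Carpal Tunnel scores between the two groups".

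No pain VAS is planned before surgery. The first one is retrospective: "After the procedure, participants will complete a short questionnaire (VAS) about any pain experienced during the administration of the local anesthetic". It is recorded after allocation and asks about an injection that differs between the arms, so it is an outcome and cannot serve as a baseline.

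On allocation, Methods says only that each patient will "be randomized to standard vs. bupivacaine treatment based on a computer algorithm". No stratification by baseline symptoms is described.

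**The concern.** Pain over the first 24 hours is the study's stated aim, and VAS is how it is measured. If the baseline score predicts post-operative VAS, an analysis that ignores it leaves explainable variation in the error term and gives a wider interval than necessary. Also, with no described stratification, the arms may differ by chance in baseline severity. An unadjusted difference then carries part of that imbalance, and the plan has no analysis to show how much. The reported differences at 6 and 8 hours have p-values of 0.01 and 0.02, so a reader may reasonably ask whether they change when a baseline measure is taken into account.

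**Working it through.** **Inputs from the document.** Minimum sample size 128, or 64 per arm at 1:1 (Statistical analyses). Analysed groups of 67 and 72; 8-hour means 2.92 and 3.87, p = 0.02 (Results overview).

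**Inputs assumed.** The plan gives no alpha, sidedness, power, effect size, SD or baseline correlation. I take two-sided 5%, 80% power and a standardized difference d = 0.5, with a correlation ρ between baseline Boston score and post-operative VAS of 0.1 to 0.5.

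**Step 1: the plan's figure.** 128 cannot be derived from stated inputs. A two-sample t-test at d = 0.5, two-sided 5% and 80% power needs 63.8 per arm, hence 64 and 128 in total. The match suggests an unadjusted design but does not prove it: 64 per arm also gives 90% power at d = 0.577.

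**Step 2: back-calculate the 8-hour standard error.** Difference = 3.87 − 2.92 = 0.95. For p = 0.02 on 67 + 72 − 2 = 137 degrees of freedom, t = 2.354. SE = 0.95 / 2.354 = 0.4036. SD = 0.4036 / √(1/67 + 1/72) = 0.4036 / 0.1697 = 2.38. This assumes a pooled t-test and takes the rounded p-value at face value.

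**Step 3: effect of adjustment.** ANCOVA multiplies the residual variance by 1 − ρ² and the SE by √(1 − ρ²). Power is recomputed at 64 per arm with d replaced by 0.5 / √(1 − ρ²), ignoring the single degree of freedom lost. The equivalent unadjusted sample size is 64 / (1 − ρ²).

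| ρ | 1 − ρ² | Power, 64 per arm | Equivalent unadjusted n per arm | 8-hour SE |
|---|---|---|---|---|
| 0 | 1.00 | 80.1% | 64 | 0.404 |
| 0.1 | 0.99 | 80.5% | 64.6 | 0.402 |
| 0.2 | 0.96 | 81.7% | 66.7 | 0.395 |
| 0.3 | 0.91 | 83.7% | 70.3 | 0.385 |
| 0.5 | 0.75 | 90.0% | 85.3 | 0.350 |

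Under the alternative reading of 128 (90% power at d = 0.577), power would rise to 91.1% at ρ = 0.2 and 96.3% at ρ = 0.5.

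**Step 4: chance imbalance.** If the arms differ at baseline by 1.96 standard errors, the unadjusted difference shifts by ρ × 1.96 × SE. At 8 hours:

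- ρ = 0.2: 0.2 × 1.96 × 0.4036 = 0.16 points, 17% of the reported 0.95
- ρ = 0.3: 0.24 points, 25%
- ρ = 0.5: 0.40 points, 42%

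Given such an imbalance, the type I error of the unadjusted test is about 6.3%, 7.9% and 12.9% respectively. Averaged over all randomizations it remains 5%. An imbalance of 1.96 SE is an unfavourable case, exceeded in either direction in about 5% of randomizations.

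**The case against.** The strongest reply is that nothing is wrong with the planned test. It is unbiased under randomization, and patient characteristics will be described by arm, so an imbalance could be seen even if not corrected. The whole benefit rests on a correlation that the documents do not supply. The Boston score is taken before surgery; the VAS measures pain in the hours and days after it. Nothing in the document links the two, and at a correlation of 0.1 the gain is 0.4 power points. All of this stands, and it limits the point to an inexpensive improvement of uncertain size.

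A reader might infer more in four ways, none of which the documents support:

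- *That the reported results at 6 and 8 hours are unreliable.* No baseline imbalance is reported, and p-values of 0.01 and 0.02 are not evidence of one.
- *That adjusting for the Boston score corrects for pre-operative pain.* Adjustment deals only with the covariate measured. The document does not describe the questionnaire's content, and no pre-operative pain score exists.
- *That operating surgeon should also be a covariate.* Methods says the surgeon "will draw up and mix the pre-determined anesthetic for each patient" and allows for two surgeons, but nothing shows that pain differs between them.
- *That ANCOVA should now replace the t-test as the main analysis.* The document already contains results, so that would be a post hoc change of main analysis.

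The proposal also leaves a separate matter untouched: patients with both sides released receive the alternate anesthetic on the second side, and a plain ANCOVA does not handle that pairing.

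**Conclusion.** The point holds as one of efficiency and of protection against chance imbalance on a baseline that is already measured. Under the assumed design (d = 0.5, two-sided 5%, 64 per arm), the gain is between 0.4 power points (ρ = 0.1) and 9.9 (ρ = 0.5), and the 8-hour SE falls by between 0.5% and 13.4%. Where the truth lies in that range cannot be settled from the document, and a gain close to nil is possible. The case for acting is that little is lost if the correlation is negligible, while a moderate one is worth several patients per arm: about 6 at ρ = 0.3 (70.3 − 64) and 21 at ρ = 0.5 (85.3 − 64).

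**What to change.** For prospective use, replace the t-test for VAS at each time point with ANCOVA, or the equivalent repeated-measures model. Include the baseline Boston score as a pre-specified covariate, state which score is meant, and report the unadjusted t-test alongside. For the data already reported, keep the planned test as the main analysis and add the adjusted estimates as a sensitivity analysis labelled post hoc.

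The cost is a sentence or two of SAP wording, about one degree of freedom, and a simple imputation rule for a missing baseline. No new data are needed.

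Optionally, and only in a future trial, add a pain VAS line to the baseline form, completed before the anesthetic is injected, and use it as the covariate. That is new data and cannot be recovered for this trial. It may predict post-operative pain better than the Boston score, but the document offers no way to check.
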